4.6.2 Patient Discontinuation from Study

Patients have the right to voluntarily withdraw from the study at any time for any reason. In addition, the investigator has the right to withdraw a patient from the study at any time.

Reasons for patient discontinuation from the study may include, but are not limited to, the following:

- Patient withdrawal of consent
- Study termination or site closure
- Adverse event
- Loss to follow-up
- Patient non-compliance, defined as failure to comply with protocol requirements as determined by the investigator or Sponsor

Every effort should be made to obtain information on patients who withdraw from the study. The primary reason for withdrawal from the study should be documented on the appropriate eCRF. Patients who withdraw from the study will not be replaced.

If a patient withdraws from the study, the study staff may use a public information source (e.g., county records) to obtain information about survival status.

4.6.3 Study Discontinuation

The Sponsor has the right to terminate this study at any time. Reasons for terminating the study may include, but are not limited to, the following:

- The incidence or severity of adverse events in this or other studies indicates a potential health hazard to patients.
- Patient enrollment is unsatisfactory.

The Sponsor will notify the investigator if the Sponsor decides to discontinue the study.

4.6.4 Site Discontinuation

The Sponsor has the right to close a site at any time. Reasons for closing a site may include, but are not limited to, the following:

- Excessively slow recruitment
- Poor protocol adherence
- Inaccurate or incomplete data recording
- Non-compliance with the International Council for Harmonisation (ICH) guideline for Good Clinical Practice
- No study activity (i.e., all patients have completed the study and all obligations have been fulfilled)

5. ASSESSMENT OF SAFETY

5.1 SAFETY PLAN

A safety plan for each treatment arm, including a summary of risks and management guidelines for patients who experience specific adverse events, is provided in the respective appendix for that treatment arm, as outlined in [Appendix 5](#), [Appendix 7](#) and [Appendix 8](#).

Measures will be taken to ensure the safety of patients participating in this study, including the use of stringent inclusion and exclusion criteria and close monitoring of patients during the study. Guidelines for managing patients who experience anticipated adverse events, including criteria for dosage modification and treatment interruption or discontinuation, are provided in [Appendix 5](#) through [Appendix 8](#). See Sections [5.2–5.6](#) for details on safety reporting (e.g., adverse events, pregnancies) for this study.

Patients with active infection will be excluded from study participation. In the setting of a pandemic or epidemic, screening for active infections (including SARS-CoV-2) prior to and during study participation should be considered according to local or institutional guidelines or guidelines of applicable professional societies (e.g., American Society of Clinical Oncology or European Society for Medical Oncology).

Severe COVID-19 appears to be associated with a CRS involving the inflammatory cytokines IL-6, IL-10, IL-2, and IFN- γ (Merad and Martin 2020). If a patient develops suspected CRS during the study, a differential diagnosis should include COVID-19, which should be confirmed or refuted through assessment of exposure history, appropriate laboratory testing, and clinical or radiologic evaluations per investigator judgment. If a diagnosis of COVID-19 is confirmed, the disease should be managed as per local or institutional guidelines.

5.2 SAFETY PARAMETERS AND DEFINITIONS

Safety assessments will consist of monitoring and recording adverse events, including serious adverse events and adverse events of special interest, performing protocol-specified safety laboratory assessments, measuring protocol-specified vital signs, and conducting other protocol-specified tests that are deemed critical to the safety evaluation of the study.

Certain types of events require immediate reporting to the Sponsor, as outlined in Section [5.4](#).

5.2.1 Adverse Events

According to the ICH guideline for Good Clinical Practice, an adverse event is any untoward medical occurrence in a clinical investigation subject administered a

pharmaceutical product, regardless of causal attribution. An adverse event can therefore be any of the following:

- Any unfavorable and unintended sign (including an abnormal laboratory finding), symptom, or disease temporally associated with the use of a medicinal product, whether or not considered related to the medicinal product
- Any new disease or exacerbation of an existing disease (a worsening in the character, frequency, or severity of a known condition) (see Sections 5.3.5.9 and Section 5.3.5.10 for more information)
- Recurrence of an intermittent medical condition (e.g., headache) not present at baseline
- Any deterioration in a laboratory value or other clinical test (e.g., ECG, X-ray) that is associated with symptoms or leads to a change in study treatment or concomitant treatment or discontinuation from study treatment
- Adverse events that are related to a protocol-mandated intervention, including those that occur prior to assignment of study treatment (e.g., screening invasive procedures such as biopsies)

5.2.2 Serious Adverse Events (Immediately Reportable to the Sponsor)

A serious adverse event is any adverse event that meets any of the following criteria:

- Is fatal (i.e., the adverse event actually causes or leads to death)
- Is life threatening (i.e., the adverse event, in the view of the investigator, places the patient at immediate risk of death)

This does not include any adverse event that, had it occurred in a more severe form or was allowed to continue, might have caused death.

- Requires or prolongs inpatient hospitalization (see Section 5.3.5.11)
- Results in persistent or significant disability/incapacity (i.e., the adverse event results in substantial disruption of the patient's ability to conduct normal life functions)
- Is a congenital anomaly or birth defect in a neonate or infant born to a mother exposed to study treatment
- Is a significant medical event in the investigator's judgment (e.g., may jeopardize the patient or may require medical/surgical intervention to prevent one of the outcomes listed above)

The terms "severe" and "serious" are not synonymous. Severity refers to the intensity of an adverse event (e.g., rated as mild, moderate, or severe, or according to NCI CTCAE; see Section 5.3.3); the event itself may be of relatively minor medical significance (such as severe headache without any further findings).

Severity and seriousness need to be independently assessed for each adverse event recorded on the eCRF.

Serious adverse events are required to be reported by the investigator to the Sponsor immediately (i.e., no more than 24 hours after learning of the event; see Section 5.4.2 for reporting instructions).

5.2.3 Adverse Events of Special Interest (Immediately Reportable to the Sponsor)

Adverse events of special interest are required to be reported by the investigator to the Sponsor immediately (i.e., no more than 24 hours after learning of the event; see Section 5.4.2 for reporting instructions). Adverse events of special interest for each treatment arm are listed in the respective appendix for that treatment arm, as outlined in Appendix 7 and Appendix 8.

5.3 METHODS AND TIMING FOR CAPTURING AND ASSESSING SAFETY PARAMETERS

The investigator is responsible for ensuring that all adverse events (see Section 5.2.1 for definition) are recorded on the Adverse Event eCRF and reported to the Sponsor in accordance with instructions provided in this section and in Sections 5.4–5.6).

For each adverse event recorded on the Adverse Event eCRF, the investigator will make an assessment of seriousness (see Section 5.2.2 for seriousness criteria), severity (see Section 5.3.3), and causality (see Section 5.3.4).

5.3.1 Adverse Event Reporting Period

Investigators will seek information on adverse events at each patient contact. All adverse events, whether reported by the patient or noted by study personnel, will be recorded in the patient's medical record and on the Adverse Event eCRF.

After informed consent has been obtained but prior to initiation of study treatment, only serious adverse events caused by a protocol-mandated intervention (e.g., invasive procedures such as biopsies, discontinuation of medications) should be reported (see Section 5.4.2 for instructions for reporting serious adverse events).

After initiation of study treatment, all adverse events will be reported until 30 days after the final dose of study treatment or until initiation of new systemic anti-cancer therapy, whichever occurs first, and serious adverse events and adverse events of special interest will continue to be reported until ■■■ days after the final dose of study treatment or until initiation of new systemic anti-cancer therapy, whichever occurs first.

Instructions for reporting adverse events that occur after the adverse event reporting period are provided in Section 5.6.

5.3.2 Eliciting Adverse Event Information

A consistent methodology of non-directive questioning should be adopted for eliciting adverse event information at all patient evaluation timepoints. Examples of non-directive questions include the following:

"How have you felt since your last clinic visit?"

"Have you had any new or changed health problems since you were last here?"

5.3.3 Assessment of Severity of Adverse Events

The adverse event severity grading scale for the NCI CTCAE (v5.0) will be used for assessing adverse event severity. Table 7 will be used for assessing severity for adverse events that are not specifically listed in the NCI CTCAE.

Table 7 Adverse Event Severity Grading Scale for Events Not Specifically Listed in NCI CTCAE

Grade	Severity
1	Mild; asymptomatic or mild symptoms; clinical or diagnostic observations only; or intervention not indicated
2	Moderate; minimal, local, or non-invasive intervention indicated; or limiting age-appropriate instrumental activities of daily living ^a
3	Severe or medically significant, but not immediately life-threatening; hospitalization or prolongation of hospitalization indicated; disabling; or limiting self-care activities of daily living ^{b, c}
4	Life-threatening consequences or urgent intervention indicated ^d
5	Death related to adverse event ^d

NCI CTCAE = National Cancer Institute Common Terminology Criteria for Adverse Events.

Note: Based on the most recent version of NCI CTCAE (v5.0), which can be found at: http://ctep.cancer.gov/protocolDevelopment/electronic_applications/ctc.htm

^a Instrumental activities of daily living refer to preparing meals, shopping for groceries or clothes, using the telephone, managing money, etc.

^b Examples of self-care activities of daily living include bathing, dressing and undressing, feeding oneself, using the toilet, and taking medications, as performed by patients who are not bedridden.

^c If an event is assessed as a "significant medical event," it must be reported as a serious adverse event (see Section 5.4.2 for reporting instructions), per the definition of serious adverse event in Section 5.2.2.

^d Grade 4 and 5 events must be reported as serious adverse events (see Section 5.4.2 for reporting instructions), per the definition of serious adverse event in Section 5.2.2.

The ASTCT CRS Consensus Grading Scale (see Table 8) should be used in addition to NCI CTCAE when reporting severity of CRS (see Section 5.3.5.1 for details on CRS reporting).

Table 8 ASTCT CRS Consensus Grading Scale

Grade	Symptom(s)
1	
 • Fever^a, with or without constitutional symptoms • No hypotension • No hypoxia
2	
 • Fever^a combined with at least one of the following: 
 – Hypotension not requiring vasopressors – Hypoxia requiring low-flow oxygen^b by nasal cannula or blow-by
3	
 • Fever^a combined with at least one of the following: 
 – Hypotension requiring one vasopressor, with or without vasopressin – Hypoxia requiring high-flow oxygen^b by nasal cannula, face mask, non-rebreather mask, or Venturi mask
4	
 • Fever^a combined with at least one of the following: 
 – Hypotension requiring multiple vasopressors (excluding vasopressin) – Hypoxia requiring oxygen by positive pressure (e.g., CPAP, BiPAP, intubation, and mechanical ventilation)
5	
 • Death due to CRS for which the cause is not the principal factor leading to this outcome

ASTCT=American Society for Transplantation and Cellular Therapy; BiPAP=bi-level positive airway pressure; CPAP=continuous positive airway pressure; CRS=cytokine release syndrome.

^a Fever is defined as temperature $\geq 38^{\circ}\text{C}$ not attributable to any other cause. In patients who develop CRS and then receive antipyretic, anti-cytokine, or corticosteroid therapy, fever is no longer required when determining CRS severity (grade). In this case, the CRS grade is driven by the presence of hypotension and/or hypoxia.

^b Low flow is defined as oxygen delivered at ≤ 6 mL/min, and high flow is defined as > 6 L/min.

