2. OBJECTIVES AND ENDPOINTS

This study will evaluate the efficacy, safety, and pharmacokinetics of multiple treatment combinations in patients with advanced GC or GEJC. Specific objectives and corresponding endpoints for the study are outlined below for Stage 1 (see Table 2) and Stage 2 (see Table 3).

Table 2 Objectives and Corresponding Endpoints for Stage 1

Primary Efficacy Objective	Corresponding Endpoint

 To evaluate the efficacy of treatment combinations during Stage 1 	
 ORR, defined as the proportion of patients with a complete response or a partial response on two consecutive occasions ≥ 4 weeks apart during Stage 1, as determined by the investigator according to RECIST v1.1
Secondary Efficacy Objective	Corresponding Endpoints

 To evaluate the efficacy of treatment combinations during Stage 1 	
 PFS after randomization, defined as the time from randomization to the first occurrence of disease progression or death from any cause (whichever occurs first) in Stage 1, as determined by the investigator according to RECIST v1.1 OS after randomization, defined as the time from randomization to death from any cause, regardless of stage OS at specific timepoints (e.g., 6 and 12 months) DOR, defined as the time from the first occurrence of a documented objective response to disease progression or death from any cause (whichever occurs first) in Stage 1, as determined by the investigator according to RECIST v1.1 Disease control rate, defined as the proportion of patients with stable disease for ≥ 12 weeks or a complete or a partial response, as determined by the investigator according to RECIST v1.1
Safety Objective	Corresponding Endpoint

 To evaluate the safety of treatment combinations during Stage 1 	
 Incidence and severity of adverse events, with severity of all events graded according to NCI CTCAE v5.0 and severity for CRS also graded according to the ASTCT CRS Consensus Grading Scale

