6.5 SAFETY ANALYSES

Safety will be assessed through summaries of adverse events, changes in laboratory test results, changes in vital signs and ECGs, and exposure to study drugs. Exposure to combination treatment and length of safety follow-up will be summarized by treatment arm within each stage.

All verbatim adverse event terms will be mapped to Medical Dictionary for Regulatory Activities thesaurus terms, and adverse event severity will be graded according to NCI CTCAE v5.0, and severity of CRS will also be graded by the investigator according to the ASTCT Consensus Grading (Lee et al. 2019). All adverse events, serious adverse events, adverse events leading to death, adverse events of special interest, and adverse events leading to study treatment discontinuation that occur on or after the first dose of study treatment (i.e., treatment-emergent adverse events) will be summarized by mapped term, appropriate thesaurus level, and severity grade. For events of varying severity, the highest grade will be used in the summaries. Deaths and causes of death will be summarized.

Relevant laboratory, vital sign (pulse rate, respiratory rate, blood pressure, pulse oximetry, and temperature), and ECG data will be displayed by time, with grades identified where appropriate. Additionally, a shift table of selected laboratory tests will be used to summarize the baseline and maximum postbaseline severity grade. Changes in vital signs and ECGs will be summarized.

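### Two internal errors in the ASTCT grading table for cytokine release syndrome: the oxygen-flow limits use different units, and the Grade 5 wording contradicts itself

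*Combined protocol and SAP*

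**What the plan says.** Section 5.3.3 tells investigators that Table 8 "should be used in addition to NCI CTCAE when reporting severity of CRS". The hypoxia criteria in that table depend on oxygen flow:

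- Grade 2: "Hypoxia requiring low-flow oxygen^b by nasal cannula or blow-by"
- Grade 3: "Hypoxia requiring high-flow oxygen^b by nasal cannula, face mask, non-rebreather mask, or Venturi mask"

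Both refer to footnote b, which reads: "Low flow is defined as oxygen delivered at ≤ 6 mL/min, and high flow is defined as > 6 L/min". Grade 1 requires that there be no hypoxia. The Grade 4 hypoxia criterion requires positive-pressure oxygen and does not use the footnote. Grade 5 is worded: "Death due to CRS for which the cause is not the principal factor leading to this outcome".

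The ASTCT grade is part of a stated endpoint. The Stage 1 safety endpoint in Section 2, Table 2 includes "severity for CRS also graded according to the ASTCT CRS Consensus Grading Scale", and Table 3 repeats this for Stage 2. Section 6.5 (Safety Analyses) states that "severity of CRS will also be graded by the investigator according to the ASTCT Consensus Grading" and cites the publication of the scale, which is listed in Section 10.

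**The concern.** Footnote b is the only place in the readable text that separates Grade 2 from Grade 3 hypoxia, and its two limits are in different units. Most of the range that the two categories ought to share then belongs to neither. The Grade 5 cell gives a cause of death and withdraws it in the same sentence.

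What is at stake is consistent ASTCT grading across sites. Section 6.5 summarizes adverse events by severity and uses the highest grade reached. Section 3.1.5 has the Internal Monitoring Committee review cumulative data at intervals. Appendix 8 (A8-2.6.2) reports more infusion-related reactions with tiragolumab plus atezolizumab in an earlier study, and Section 5.3.5.1 says these reactions can be hard to tell apart from CRS. Clear CRS grading is therefore relevant to the experimental arm.

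**Working it through.** There is no sample size, power or event figure to reproduce. The check is a unit conversion followed by a literal reading of the table.

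**Inputs** (all from Section 5.3.3, Table 8): low flow ≤ 6 mL/min; high flow > 6 L/min; the criteria for Grades 1 to 5; footnote a.

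**Step 1: conversion.** 6 mL/min ÷ 1000 = 0.006 L/min. The two limits differ by a factor of 6 ÷ 0.006 = 1000. The uncovered range runs from above 0.006 up to and including 6 L/min, a width of 6 − 0.006 = 5.994 L/min.

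**Step 2: classify test flows** as written, and with each possible common unit.

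| Flow (L/min) | As written | Both limits in L/min | Both limits in mL/min |
|---|---|---|---|
| 0.006 | low | low | low |
| 0.01 | neither | low | high |
| 0.5, 1, 2, 4, 6 | neither | low | high |
| 6.1, 10, 15 | high | high | high |

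Either common unit closes the gap, but the two choices give different answers. For nasal oxygen at 0.5 to 6 L/min, one gives a Grade 2 hypoxia criterion and the other Grade 3.

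**Step 3: one literal case.** Take a patient with fever, hypoxia on 2 L/min by nasal cannula, and no hypotension.

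- Grade 1 fails, because hypoxia is present.
- Grade 2 fails, because 2 L/min exceeds 0.006 L/min and there is no hypotension.
- Grade 3 fails, because 2 L/min does not exceed 6 L/min and there is no hypotension.
- Grade 4 fails, because there is no positive pressure and no hypotension.

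Footnote a removes the fever requirement once antipyretic, anti-cytokine or corticosteroid therapy has been given. Hypotension and hypoxia alone then set the grade, so the gap remains.

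**Step 4: what stays gradable.** Grades 2 to 4 each need at least one of a hypotension or a hypoxia criterion. A patient with qualifying hypotension therefore receives a grade on that criterion. So does a patient whose oxygen exceeds 6 L/min by a listed route, or who needs positive pressure.

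**Step 5: Grade 5.** The first clause says the death is due to CRS. The qualifier says the cause is not the main contributor to that outcome. If the cause is CRS, the clauses conflict. If it is something else, the cell does not say what. The fault is in the wording and no arithmetic applies.

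**Step 6: weight of one case.** Section 3.1.2 plans 20 patients in the experimental arm, or 20 + 25 = 45 with expansion. One case is 1/20 = 5% or 1/45 = 2.2% of that arm. The documents give no CRS rate, so the number of affected cases cannot be estimated.

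**The case against.** The strongest reply is that the table is a flawed copy of a named, cited scale used as a second instrument. Every CRS event also receives a CTCAE grade. A fatal event is a serious adverse event under Section 5.2.2, and Section 5.3.5.8 requires deaths not attributed solely to disease progression to be recorded and reported during the reporting period. The numeral 6 appears on both sides of footnote b with complementary signs, so most investigators would see a single cut-off with a stray prefix. The safety analysis is descriptive, Section 6.1 disclaims power and type I error considerations, and Section 3.1.3 lists no available Stage 2 treatment, so at present the endpoint operates only in Stage 1. Appendix 5, which holds the CRS management guidance, is redacted and may restate the limits correctly.

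All of this stands as a limit on the consequence. It does not remove the error. A CTCAE grade does not supply a missing ASTCT grade. Section 5.3.3 sends investigators to Table 8, so that is the text sites work from, and citing the source helps only if each site consults it. Reading the footnote as a slip depends on every site making the same silent repair, and Step 2 shows that the choice of unit changes the grade.

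**Conclusion.** Both errors are in the current, intact text, and the table is wrong as written. This is an internal inconsistency, not a design choice. Read literally, CRS with hypoxia on more than 0.006 and up to 6 L/min, without qualifying hypotension, meets none of ASTCT Grades 1 to 4, and Grade 5 contradicts itself. The effect is limited to the ASTCT component of the CRS severity endpoint.

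The documents do not support three stronger readings that a reader might infer:

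- **That these events, or fatal CRS, cannot be graded or would be lost.** CTCAE grading and serious adverse event and death reporting continue regardless, and the routes in Step 4 remain open.
- **That the between-arm safety comparison is altered.** No case count is given, no formal safety test is planned, and actual misgrading has not been shown. Objective response rate and the sample size do not depend on this table.
- **That Grade 5 deliberately excludes deaths caused mainly by CRS.** That is one literal reading of garbled wording. Table 7 in the same section treats Grade 5 as death related to the event.

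The conclusion rests on a literal reading of Table 8. That few cases will arise is an assumption. Whether Appendix 5 repeats or corrects the limits cannot be determined from the public text.

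**What to change.** Correct footnote b and the Grade 5 cell against the scale cited in Section 6.5 and listed in Section 10. Both flow limits should be in one unit and meet at one value, and the Grade 5 qualifier should agree with the attribution of the death to CRS. The unit and wording should come from that source, since the protocol's own text cannot settle them. Then confirm that Appendix 5 and the dedicated CRS eCRF (Section 5.3.5.1) carry the same definitions, and re-check the ASTCT grade of any CRS event already recorded.

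The text change is one footnote and one table cell. The full cost is a minor protocol amendment under Section 9.6 and a short data check. No treatment rule, endpoint definition or analysis method needs to change.
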